In the current study, we will examine how the *Surviving and Thriving in the Real World (STRW)* intervention improves the DLS of 72 adolescents with ASD in their last 2 years of high school. Our previous work has found that STRW can increase the DLS of adolescents with ASD by 2-2.5 years over the course of the intervention, which has significant and practical implications for both current functioning (e.g., maintaining a part-time job while in high school, managing a checking and savings account, cooking meals for oneself) and future adult outcomes (e.g., budgeting for monthly expenses, keeping one's apartment clean, making routine medical appointments, planning for meals for an entire week and then going grocery shopping). The current study will examine these outcomes and also explore how factors such as social-communication skills (e.g., understanding expectations, taking others' perspectives), executive functioning abilities (e.g., getting started on tasks, organizing, managing time), and parenting and family factors (e.g., parental stress, over-involvement in daily routines) may affect one's ability to acquire DLS.

PURPOSE OF STUDY:

The main objective of the current proposal is to conduct a pilot RCT (i.e., treatment group and social skills control group) to examine how participation in STRW affects proximal outcomes with a larger sample size (n = 70). As social skills, executive functioning, and parenting factors have been linked to the acquisition of DLS, the current study will also explore how these are linked to participation in STRW. Lastly, goal attainment scaling (GAS) will be utilized, along with gold standard parent report and adolescent self-report measures, to assess DLS.

Aim 1: Examine the effectiveness of Surviving and Thriving in the Real World (STRW) in a pilot RCT. Participants will be randomized to STRW or a social skills control group (Program for the Evaluation and Enrichment of Relational Skills-PEERS). The STRW group will show significant improvement on the Vineland Adaptive Behavior Scales, 3rd Edition (Vineland-3) and progress on targeted DLS using goal attainment scaling (GAS), baseline to post-treatment, as compared to the control group.

Aim 2: Assess the maintenance of treatment gains 6-months after completion of STRW. Participants in the STRW group will continue to show significant improvement on the Vineland-3 and progress on targeted DLS using GAS, baseline to 6-month follow-up, as compared to the control group.

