Aim 3 (Exploratory): Examine how social skills, executive functioning, and parenting and family factors, which have all been linked to DLS, are affected by participation in STRW.

BACKGROUND:

Individuals with high functioning autism spectrum disorder (ASD) are not developing the skills necessary to successfully transition from adolescence to college, employment, and independent living. Recent studies(Centers for Disease Control and Prevention, 2014; Charman et al., 2011; Christensen et al., 2016) have found that nearly 50% of individuals with ASD can be classified as high functioning (i.e., IQ >70), and 25% have IQs in at least the average range (i.e., IQ >85). Despite their cognitive abilities, the outcomes of living independently, attending college, and being employed for adults with high functioning ASD are extremely bleak(Henninger & Taylor, 2013) as they are less likely to be engaged in any vocational or educational activities after high school even as compared to individuals with ASD and a comorbid intellectual disability (Taylor & Seltzer, 2011). A recent review of adult outcomes found that 50% of adults with high functioning ASD are living with their parents and require significant supports with everyday activities (Magiati, Tay, & Howlin, 2014). Individuals with high functioning ASD are uniquely at risk for struggling with attending and graduating from college and obtaining and maintaining a job even when compared to youth with intellectual disabilities(Shattuck et al., 2012). One study found that only 12% of individuals with high functioning ASD attended a 4-year college (Shattuck et al., 2012). Further, only 50-55% of adults with high functioning ASD are employed in full or part-time jobs(Barneveld, Swaab, van Engeland, & de Sonneville, 2014; Farley et al., 2009) and little is known about factors that prevent them from obtaining employment or being underemployed (Walsh, Lydon, & Healy, 2014). A study that examined the outcomes of adults with ASD within 4 years of graduating high school found that nearly one quarter of adults with high functioning ASD were not participating in any vocational, postsecondary, or community activities during the day, a rate 3 times higher than those with ASD and a comorbid intellectual disability(Taylor & Seltzer, 2011). These poor outcomes are startling because parents and professionals often expect individuals with high functioning ASD to successfully transition to the adult world because of their intact cognitive abilities and less severe profile of ASD symptomatology. Thus, it is critical to develop interventions that will lead to success in college, employment, and independent living(Chakrabarti & Fombonne, 2001).

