or the ADOS-2, either clinically or for a previous study, record of this exam including scoring may be utilized in this project if the results are considered acceptable for use by the Principal Investigator (i.e., completed within the last 2 years, completed by a psychologist who is research reliable on the ADOS-2). The parent participants will complete the Vineland-3 to confirm that their adolescent has deficient daily living skills (i.e., 15 points below their full scale IQ in 1 of the 3 Daily Living Skills subdomains) and a clinical interview that assesses specific daily living skills that will be targeted in the STRW intervention. The baseline assessment will include parent questionnaires, a parent interview, and an adolescent assessment (in which they will also complete questionnaires) and will take approximately 2-3 hours for both parent and adolescent participants to complete. All procedures for the baseline visit except for the ADOS and the IQ test may be conducted via telehealth. Information about medication usage and services/therapies received at home, school, or community will be collected at each assessment. The parent interview will be audio or video taped to assist in the development of goals using the method of goal attainment scaling (GAS). If inclusion criteria is met, participants will then be randomized to either the STRW group or the social skills group.

Post-Treatment and 6-Month Follow-up.

The post-treatment and 6-month follow-up assessments will include parent questionnaires, a parent interview, and adolescent questionnaires and will take approximately 60-90 minutes for both parent and adolescent participants to complete. All procedures for the post-treatment and 6 month follow up visits may be conducted via telehealth. Information about medication usage and services/therapies received at home, school, or community will be collected at each assessment. The parent interview will be audio or video taped to assist in the development of goals using the method of goal attainment scaling (GAS).

The STRW treatment group and the PEERS control group will complete 3 research assessments (baseline, post treatment, and 6 month follow up).

12-Month, 18-Month, and 24-Month Parent Follow-Up

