The *Adaptive Behavior Assessment System, 3rd Edition (ABAS-III)(Harrison & Oakland, 2015)* is a parent and self-report measure that assesses adaptive behavior in the conceptual, practical, and social domains. The raw scores and T-scores will be utilized to compare parent and adolescent ratings of DLS.

The *Behavior Rating Inventory for Executive Function, 2nd Edition (BRIEF-2)* (Giola, Isquith, Guy, & Kenworthy, 2000) is a parent and self-report measure that assesses executive functioning across 8 scales including initiate, emotional control, shift, inhibit, organize/plan, organization of materials, and working memory. Raw scores for the scales and indices will be utilized to explore the relationship between executive function and participation in the intervention.

The **Social Responsiveness Scale**, **2**nd **Edition** (**SRS-2**)(Constantino, 2012) is a 65-item parent-report measure that assesses social functioning in the areas of social awareness, social cognition,

social communication, social motivation, and restricted interests and repetitive behavior. Raw scores and T-scores will be utilized to explore the relationship between social skills and participation in the intervention.

The *Behavior Assessment Scale for Children, 3rd Edition (BASC-3)* (Kamphaus & Reynolds, 2015), is a comprehensive set of rating scales and forms including the Teacher Rating Scales (TRS), Parent Rating Scales (PRS), Self-Report of Personality (SRP), Student Observation System (SOS), and Structured Developmental History (SDH). Together, they help you understand the behaviors and emotions of children and adolescents. This study will utilize the Parent Rating Scales (BASC-3 PRS Adolescent), the Self-Report of Personality (BASC-3 SRP Adolescent), and the Parent Relationship Questionnaire (BASC-3 PRQ Child/Adolescent).

The *Helicopter Parenting Questionnaire*(Padilla-Walker & Nelson, 2012) will be completed by adolescents and their parents and was adapted from another questionnaire. Five items, rated on a 5-point scale, assess parental involvement in making important decisions (e.g., solves any problem, intervenes in settling disputes with teachers). The raw score will explore the relationship between parental expectations and participation in the intervention.

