The *Parental Expectations Questionnaire*(H. M. Chiang, Cheung, Hickson, Xiang, & Tsai, 2012) will be completed by parents and was developed from the National Longitudinal Transition Study-2 to assess parental expectations in the areas of education, postsecondary school completion, and independence. Each item is scored on a 4-point Likert scale and the raw score will explore the relationship between expectations and participation in the intervention.

The **Family Quality of Life (FQOL) scale**(Hoffman, Marquis, Poston, Summers, & Turnbull, 2006) will be completed by parents and has 5 domains that assess family interaction, parenting, emotional well-being, physical/material well-being, and disability related support. Each of the 25 items is scored on a 5-point Likert scale and the raw score on each domain will explore the relationship between family quality of life and participation in the intervention.

The Community Integration Scale is a 33-item measure that documents a person's involvement in their community. There is a parent version for their child, and a self-report version.

Child Concentration Inventory, Second Edition (CCI-2). The CCI-2 (Becker, 2015) is a child-report measure of SCT symptoms. The CCI-2 consists of 16 items that are rated on a four-point scale (0 = never, 1 = sometimes, 2 = often, 3 = always). There is evidence supporting the reliability and validity of the CCI-2 in children and adolescence (Sáez, Servera, Burns, & Becker, under review).

Child and Adolescent Behavior Inventory (CABI). The CABI SCT module was derived from a meta-analysis which examined the stability and reliability of SCT items derived from various measures (Becker et al., 2016). Parents will complete the CABI (Burns, Lee, Servera, McBurnett, & Becke, 2015) SCT module. Recent studies support the reliability and validity of the CABI (Becker, Burns, Schmitt, Epstein, & Tamm, 2017; Sáez, Servera, Becker, & Burns, 2018).

The Social Skills Improvement System (SSIS). The SSIS (Gresham, 2008) is a parent and self-report measure that assesses social skills (i.e., communication, responsibility, self-control, cooperation), competing problem behaviors (e.g., externalizing, internalizing, bullying), and academic competence (e.g., motivation to learn). Raw scores and standard scores will be utilized to explore the relationship between social skills and participation in the intervention.

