decreased motivation from teen to work on DLS, developing parental skills to foster independence with DLS, identifying rewards to increase the likelihood of continued skill development) and assist in problem-solving these barriers.

STRW Telehealth Sessions: The STRW parent sessions will be facilitated via video, using the HIPAA compliant version of Zoom. The format will be similar to the in-person sessions.

The STRW teen sessions will be scheduled and run by a psychology post-doctoral fellow or graduate student trainee. The sessions will be scheduled for 1 hour, and both parent and teen will participate. Targeted daily living skills will be practiced using the participant's home appliances and materials.

The PI will provide weekly supervision to all fellows and trainees that facilitate the STRW adolescent sessions. Both in-person and telehealth sessions will be videotaped and coded for treatment adherence and fidelity. A blinded coder will complete a treatment adherence and fidelity checklist on 25% of the sessions chosen at random.

PEERS Control Group:

Due to COVID-19, an undetermined number of sessions will be conducted via telehealth using a HIPAA approved version of Zoom.

PEERS In-Person Sessions: PEERS is the control group and consists of 14 weekly (90 minute) concurrent sessions that both adolescents with ASD and their parents attend. Social-communication and interaction skills such as building friendships, handling arguments, dealing with teasing, arranging and attending outings with peers are targeted through direct instruction, modeling, and practice in adolescent sessions. Parents are taught how to build and reinforce social skills outside of sessions. The purpose of the control group is to allow us to assess change in daily living skills in a group of high functioning adolescents with ASD who have deficient daily living skills but do not receive systematic behavioral treatment targeting specific skills using evidence based strategies.

PEERS Telehealth Sessions: The PEERS parent and teen sessions will be run simultaneously using the HIPAA compliant version of Zoom. This will require families to have two devices so both parent and teen can attend sessions at the same time.

DURATION:

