To test Aim 3: Exploratory analyses will be conducted to examine the relationship between progress in DLS and executive functioning, social skills, and parenting and family factors. A regression analysis will be used to estimate and examine this potential relationship. In this model the change score (post-treatment and baseline) will be modeled as a function of each of the measures of executive function, social skills and parenting and family factors. This will allow us to characterize the response profile.

Missing data methods

All missing data will be discussed and every effort will occur to ensure all data are accounted for. Parents will be given multiple opportunities to fill out parent-report forms. To minimize possible loss to follow up, we will stay in close contact with families and identify any potential barriers to successful completion. Despite these efforts, missing data may occur. We will first examine the missing pattern to determine if missingness occurs systematically and differentially for each group, and tabulate the reason for missingness. Assuming at random, we will use multiple imputation technique to generate multiple datasets and systematically combine the estimates obtained from each dataset and associated variability. We will also investigate the potential that the missingness is not at random by performing sensitivity analysis recommended for clinical studies. Suspected biases will be taken into account in the interpretation of results.

Sample Size and Power Calculations

The pilot RCT is being conducted with the intent of examining the differences in DLS to be expected. Few studies have examined the trajectory of DLS in individuals with ASD(Baghdadli et al., 2012; Bal et al., 2015; Szatmari et al., 2009), and no studies have examined how DLS develop during adolescence. Power calculations focused on the anticipated increase or improvement in the age equivalence scores of each of the Vineland-3 DLS subdomains for the STRW group and control group. We used conservative estimates of change in DLS subdomain age equivalence scores for our sample size estimation, even though a recent pre-post trial on STRW with 7 participants found a mean improvement of 2.3 to 2.6 years across the 3 subdomains(Duncan et al., in press) from baseline to post-treatment.

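### Aim 3 asks what STRW does to social skills, executive function and family factors, but its only analysis regresses DLS change on those factors with no treatment-arm term

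*Combined protocol and SAP*

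**What the plan says.** **The aim.** Under Purpose of Study, Aim 3 (exploratory) reads: "Examine how social skills, executive functioning, and parenting and family factors, which have all been linked to DLS, are affected by participation in STRW". The opening paragraph of the same section says of these factors that "the current study will also explore how these are linked to participation in STRW".

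**The measures.** The Measures section describes the use of six instruments in the same terms. For the BRIEF-2: "Raw scores for the scales and indices will be utilized to explore the relationship between executive function and participation in the intervention". For the Family Quality of Life scale: "the raw score on each domain will explore the relationship between family quality of life and participation in the intervention". The SRS-2, Helicopter Parenting Questionnaire, Parental Expectations Questionnaire and SSIS have parallel statements. All six are listed under the heading for baseline, post-treatment and 6-month follow-up.

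**The analysis.** Under Analyses, the Aim 3 paragraph says it will examine how progress in DLS relates to the factors, and then that "the change score (post-treatment and baseline) will be modeled as a function of each of the measures of executive function". The same sentence adds the measures from the social and family domains as further predictors. The paragraph closes by saying this will characterise the response profile. It names no arm term and no interaction. It does not say whether one arm or both enter, or whether the factors are baseline or change values.

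**The abstract.** This puts the question the other way round. The study will "explore how factors such as social-communication skills", executive functioning and family factors may influence the acquisition of DLS.

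**The concern.** In Aim 3 the factors are the outcomes and participation in STRW is the exposure. In the Aim 3 analysis the factors are the predictors, DLS change is the outcome, and participation is absent. These are different quantities, and the second cannot stand in for the first.

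The data for the stated aim will exist: "The STRW treatment group and the PEERS control group will complete 3 research assessments", at baseline, post-treatment and 6 months. Families complete these questionnaires at every visit, yet the plan as written produces no estimate of what STRW does to the factors. If the comparison is made later without prespecification, it is open to choice among many scales, raters and visits.

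There is a second problem. With no arm or arm-by-factor term, the planned regression cannot separate predictors of response to STRW from predictors of DLS change in general. It does not support a response profile if that means response to STRW.

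**Working it through.** The documents give no sample size, power or effect size for Aim 3, so there is no figure of the plan's own to reproduce. The check is first structural, then an illustration, then the precision of the missing comparison.

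**1. Does any planned analysis compare the arms on the factors?**

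| Analysis paragraph | Outcome | Arm comparison? |
|---|---|---|
| Aim 1 (t-test, then linear model) | Change in Vineland-3 DLS domain and GAS | Yes, but not on the factors |
| Aim 2 (paired t-test) | Change from post-treatment to 6 months in those receiving the intervention | No |
| Aim 3 (regression) | DLS change | No arm term listed |

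Instruments with a described use tied to the intervention: BRIEF-2, SRS-2, Helicopter Parenting, Parental Expectations, Family Quality of Life, SSIS. Count: 6. Planned arm comparisons among them: 0.

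**2. Could the Aim 3 regression supply the answer under some reading?**

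- Both arms pooled, no arm term: between-arm and within-arm association are mixed.
- STRW arm only: there is no comparator.
- Baseline factor values as predictors: these precede randomisation and cannot show an effect of STRW.

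The pooled, change-on-change reading can be illustrated. Let b be the STRW effect on the factor, g the STRW effect on DLS, and w the within-arm correlation, with within-arm SDs of 1 and 1:1 allocation. Then

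pooled slope = (w + b·g/4) / (1 + b²/4).

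Take g = 5/8.4 = 0.595, from the 9 versus 4 month gains and SD of 8.4 under Sample Size and Power Calculations. The values of b and w are assumptions.

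- b = 0, w = 0.4: slope = 0.40.
- b = 0.5, w = 0: slope = (0.5 × 0.595/4)/(1 + 0.25/4) = 0.0744/1.0625 = 0.07. For b = 0.3 to 0.8 the range is 0.04 to 0.10.

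The slope can be sizeable when STRW does nothing to the factor, and close to zero when it has a moderate effect.

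**3. What would an arm comparison deliver?**

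Inputs: 35 per arm (Study Design). Two-sided 0.05, a baseline-to-post correlation r of 0.5 to 0.7, and no attrition are assumptions. SE of the difference, in SD units = √(2/35) = 0.239.

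| Analysis | 95% CI half-width (SD) | Detectable at 80% power (SD) |
|---|---|---|
| Unadjusted, df 68: t(0.975) × 0.239 | 0.477 | 0.679 |
| Baseline-adjusted, r = 0.5, df 67: × √(1 − 0.25) | 0.413 | 0.588 |
| Baseline-adjusted, r = 0.7, df 67: × √(1 − 0.49) | 0.341 | 0.485 |

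Detectable differences use the noncentral t distribution. With 32 per arm, the number used in the plan's power statement, the unadjusted values are about 0.50 and 0.71 SD.

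**4. Costs of adding terms.**

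- Six independent tests at 0.05: 1 − 0.95⁶ = 0.265 chance of at least one false positive.
- Arm-by-factor interaction, factor standardised, residual SD of DLS change set to 1, df 66: SE = √(2/35) = 0.239. The slope difference detectable at 80% power is 0.680 residual SD of DLS change per SD of the factor.

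**The case against.** The strongest reply is that the abstract asks the reverse question and the Aim 3 regression answers it, so the documents conflict over what Aim 3 is. On that view, rewording Aim 3 would restore consistency with no extra models and no extra false-positive risk. The fit with the abstract is real, and the regression is a legitimate predictor analysis. But the numbered aim, the purpose statement and the described uses of the measures all refer to participation. Rewording would tidy the text while leaving unanswered a question for which both arms already supply data.

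Second, the wording in Measures, a relationship with participation, is looser than that of Aim 3 and could be read as progress during the intervention. That is fair, and it makes the count of six supporting evidence only. The aim's own wording is plainly directional and carries the point.

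Third, Aim 3 is exploratory, in a pilot, and nothing forbids an unplanned arm comparison later. This stands as a limit on severity: what the plan forgoes is a prespecified answer, not the data. Exploratory status relaxes error control, but it does not make a model estimate a quantity that it omits.

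Fourth, the precision figures assume full enrolment and an alpha that the documents do not state. Both are assumptions, and neither affects whether the mismatch exists.

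**Conclusion.** The concern holds. Carried out exactly as written, the plan gives no estimate of how STRW affects social skills, executive function or parenting and family factors, and none of the six instruments has a planned arm comparison. This is an analysis aimed at a different question from the aim, not merely a missing detail. The primary conclusions are unaffected, so the change is one that should be made rather than one on which the trial depends.

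The structural conclusion rests on the text alone. The expected precision rests on 35 analysed per arm, two-sided 0.05, an assumed r of 0.5 to 0.7, and independent observations. On that basis an added comparison would yield an estimate with a CI, not a confirmatory test.

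**What to change.** 1. **Add an exploratory between-arm comparison for each Aim 3 instrument.** Name one score in advance, including the rater where there are parent and self-report forms. Regress the post-treatment score on arm and its baseline value, and report the arm difference with a 95% CI. Treat the 6-month score likewise if wanted. State which instruments belong to Aim 3; the BASC-3 parent relationship questionnaire, for example, has no stated purpose.
2. **State the comparator for the social-skills measures.** For the SRS-2 and SSIS the contrast is with PEERS, an active programme: "Parents are taught how to build and reinforce social skills outside of sessions". No difference, or one favouring PEERS, does not show that STRW has no effect on social skills.
3. **Relabel the existing regression** as an analysis of predictors of DLS change. State which arms enter and that the factors are baseline values, since change values may themselves be altered by the arm.
4. **Only if response to STRW is to be profiled,** fit that regression in both arms with arm and arm-by-baseline-factor terms, acknowledging the weak power shown above.
5. **Label all of this exploratory,** without multiplicity control.

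The cost is one SAP paragraph and six simple models, with no new data or visits. The downside is more low-powered comparisons, with about a 26% chance of at least one false positive across six independent tests. Results should therefore be reported as estimates and CIs rather than as claims of significance.
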